The radio messaging in both intervention groups, and the short videos in the second intervention group (only) will be introduced after the baseline assessment of the caregiver cohort. The exposure period for the two interventions, as described in Table 2, will be for nine months, followed by the endline assessment of caregivers.

Table 2. Description of intervention packages in two study arms

Intervention group	Description and expected exposure (dose)
Malezi II minimum package Radio (MR)	Radio messaging spots Dose: Up to 35-40 different messages, 3 stations aired on (2 regional, 1 national), about 10 times per day; 7 days per week airing frequency; 9 months duration of exposure 
▪ Caregiver exposure to radio messaging during 9-month period: currently unknown, but estimated at 50% of caregivers hearing about 7 messages/week.
Malezi II full package Radio, Video Job Aids, CCD program (MRV-CCD)	Radio messaging spots 
▪ Same as MR group

MRV-CCD	
Short video ECD job aids (with training)
 
Five short ECD mobile films (videos) of 3-5 minutes each will feature a mixture of real-life testimonies and scripted interactions between health workers and caregivers, and demonstrations of caregivers stimulating their young child. Each video will show a range of age-appropriate ECD practices that encourage child development (play; communication; positive caregiver-child interaction; safe/stimulating environment; positive discipline), illustrating skills and providing knowledge. All videos will have some cross-cutting content, emphasizing the general benefits of ECD activities during the early years, and one video will be devoted exclusively to cross-cutting parental guidance on developmental milestones and benefits of applying ECD practices. Four videos will target specific age groups (0-5, 6-11, 12-23, >=24 months).
 
Caregiver exposure to group counseling at clinic is estimated to be 2-4 sessions in a 9-month period
 
Caregiver exposure to individual counseling at home is estimated to be 3-6 sessions in a 9-month period

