The outcome parameters used for sample size calculations for objectives 1 and 2 are estimated from the Malezi I program evaluation baseline data (before introduction of CCD program), comparable to what we would expect in the MR intervention group, who have not been exposed to any CCD intervention. From 24-29% of caregivers reported having a local or shop toy in the home, 22% reported singing to the child in the past month, and 7-13% reported reading or writing with the child in the past week.

Objective 1: To determine caregiver radio listenership patterns at baseline, and exposures to the ECD radio messaging nine months' post-intervention, and effect of radio exposure on caregiver ECD perceptions, knowledge and reported parenting practices, using pre-post surveys in a cohort of caregivers of children 0-24 months of age at baseline, in study communities from each intervention arm.

A sample size of 593 enrolled in the MR intervention group will provide 80% to detect a 5% or greater change from baseline (10%) to endline (15%) in the MR intervention group, taking into account 15% LTFU, design effect of 1.2, and estimated correlation of 0.4 between respondents at baseline and endline (Table 3). This sample size will provide even greater power to detect a 10% difference if baseline estimates are higher than 10%.

Table 3. Sample size estimation* parameters, MR group, caregiver cohort, pre-post

Arm	Prevalence of key outcome			Power	Sample size	Adjusted Sample size (15% LTFU, DE 1.2)
	Baseline	Endline	Expected Change			
MR (Malezi radio)	10%	15%	5%	80%	420	593
	20%	30%	10%	99%	419	592
	25%	35%	10%	98%	411	580

*STATA 14 paired proportions large-sample McNemar's test at 5% level significance.

Objective 2: To determine whether the Malezi II full intervention (MRV-CCD) significantly increases caregiver's knowledge and parenting behaviors/practices when compared to radio messaging alone, using a pre-post quasi-experimental evaluation design in a cohort of caregivers of children 0-24 months of age at baseline, in MRV-CCD and MR communities.

The change between baseline and endline in the Malezi I evaluation for the above-mentioned indicators ranged from 10-30% after introduction of the Malezi I CCD program. With the introduction of radio messaging only, we estimate a 5-10% effect size, and about a 20-30% effect size in the full intervention (MRV-CCD) group (Table 4).

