We estimate that a sample size of n=430 caregivers per intervention group will provide 90% power to detect a 15% "difference-in-differences" between the MR and MRV-CCD intervention groups at endline, and >80% power to detect a 5% change in the MR intervention group, and a 20% change in the MRV-CCD intervention group between baseline and endline, at a level of 5% significance. Taking into account a 15% non-retention rate and a design effect of 1.2, we will aim to enroll 1214 into the caregiver cohort or n=607 in each intervention group.

Table 4. Sample size estimation* parameters, MR compared to MRV-CCD groups, caregiver cohort, pre-post and differences-in-differences

Arm	Prevalence of key outcome			Power	Sample size	Adjusted Sample size (15% LTFU, DE 1.2)
	Baseline	Endline	Expected Change			
MR (Malezi radio)	10%	15%	5%	81%	430	607
MRV-CCCD (Malezi radio + radio + CCD program)	25%	45%	20%	>99%	430	607
Difference	15%	30%	15%	90%	860	1214

*Sample Size and Power estimated by a simulation of the DID Analysis using R Software Package.

Objective 3. To determine whether the introduction of short video job aids (training, provision, supportive supervision) to the Malezi II CCD program improves the quality of counseling provided by the CHW in the clinic and the home, using pre-post observation fidelity checklists for all CHWs working in the MRV-CCD communities.

The Malezi I evaluation assessed CHW-reported time spent in the home providing ECD messages to pregnant women or caregivers of children under 5 at baseline (14-17%) and endline (64-74%). While the change was substantial, we estimate that the actual CHW counseling skills would be lower using an observation checklist compared to CHW self-reported behaviors. We conservatively estimate that CHWs in the MRV-CCD intervention group, already trained in the Malezi I CCD program, will score at 50% on the baseline observation checklists in this evaluation, increasing 15-20% after introduction and capacity building in using the short videos.

Table 5 shows that a sample size of 123 CHWs will achieve 80% power to detect a 15% change between baseline and endline in CHW quality of counseling checklist score, taking into account a correlation of 0.4 between measures, a 5% non-retention rate and a design effect of 1.1.

Table 5. Sample size estimation* parameters, MRV-CCD CHW cohort, pre-post

Arm	Prevalence of key outcome			Power	Sample size	Adjusted Sample size (5% LTFU, DE 1.1)
	Baseline	Endline	Expected Change			

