Descriptive statistics (range, median, mean, percent) will be used to review the data overall and describe participant background characteristics, radio listenership patterns and parenting perceptions, knowledge and practices, identifying any baseline differences in population by study group. Confidence intervals (CI) will be calculated around summary measures and statistical tests of significance (non-parametric) will be applied where appropriate to compare the distribution of characteristics or outcomes across study groups. The effects of radio exposure only (objective 1) will be described by comparing study outcomes at baseline and endline within the MR study group only. Within study group differences in study outcomes will be described comparing distributions of responses to key outcome variables at baseline and endline using statistical testing appropriate for paired groups such as the paired t-test, Wilcoxon or McNemar's tests. Regression modelling may be used to estimate the intervention effect while controlling for covariates.

The additional effects of the combined exposure to radio, short videos and Malezi CCD (MRV-CCD; objective 2), as compared to the radio only effect, will be described using a differences in differences (DID) analysis. The treatment effect can be found by obtaining the proportion of caregivers with the outcome in the MRV-CCD and MR groups at both time periods. The difference in outcomes between study groups at both time periods may be charted to visualize the DID as shown in Figure 4, whereby the DID is what remains after subtracting the baseline differences between the two groups from the endline differences (30-5% = 25%). This will give an estimate of the extent of the improvement by the Malezi II full intervention. We will use regression modelling to estimate the intervention effect while controlling for covariates. We will use the following general form model:

$$Y = \beta_0 + \beta_1[\text{Intervention}] + \beta_2[\text{Time}] + \beta_3[\text{Intervention} \cdot \text{Time}] + \beta_4[\text{Covariates}] + \varepsilon$$

The interaction term coefficient β_3 will also estimate the extent of the DiD.

[figure not shown]

Figure 4. Differences in differences analysis graphic

Objective 3: Community Health Worker Cohort

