Respondents in the caregiver cohort will be offered an age-appropriate toy as an expression of thanks for their time, equivalent to less than USD 5 (~11,000 Tanzanian Shillings [Tsh]), at both baseline and endline assessments. The toy will be a locally made of soft material, such as doll, animal or book. There will be no compensation provided to caregivers at the stage I listenership survey participation. CHWs will receive transport reimbursement of <USD 5 (Tsh 10,000) for meeting the interviewer at the clinic for baseline and endline interviews and for four home visits total (Tsh 5,000 for each). CHW cohort participants joining the FGDs will receive half per diem (about Tsh 30,000 or about 13 USD equivalent) to cover costs related to travel and being away from their homes and communities for a working day, and reimbursement of their transport, if applicable, as per official receipt. This compensation is determined according to EGPAF policies and is therefore subject to minor changes.

Caregivers participating in IDIs will not receive any compensation as these interviews are taking place at their homes, and the visit will be no longer than about one hour.

TIMEFRAME

The overall evaluation is expected to take about 2 years.

POLICY/PROGRAM SIGNIFICANCE AND DISSEMINATION

Outcomes from this evaluation will inform decision makers in Tanzania about the feasibility and effectiveness of a health systems-based ECD intervention, augmented by radio communications and/or short video use. The feasibility and potential contributions of ECD short videos to CHW skills and caregiver behaviors will inform the potential scale-up of digital job aids, and is an area the Government of Tanzania has already invested in through various other digital health initiatives. While this evaluation is not designed to be generalizable to other countries or globally, we believe that the findings from this evaluation can still make substantive contributions to literature on how nurturing care (ECD) interventions can be integrated into routine MNCH and HIV care in resource-constrained settings.

Results from this evaluation will be disseminated locally through meetings with R/CHMTs, nationally with Government policy-makers and program implementers, and internationally through presentations at scientific conferences and peer-reviewed journal publication.

REFERENCES

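### The soft toy or book offered at baseline can itself raise toy, book and play-material items, so the Objective 1 radio-only change on those items mixes gift and radio, and the Objective 2 DID can be biased in either direction

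*Protocol*

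**What the plan says.** Under Risks, Benefits and Compensation, the Protocol states: "Respondents in the caregiver cohort will be offered an age-appropriate toy as an expression of thanks for their time". This happens at both assessments, at a value under USD 5. It adds: "The toy will be a locally made of soft material, such as doll, animal or book". Both arms are covered.

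Under Intervention Description, the radio messages and the videos "will be introduced after the baseline assessment of the caregiver cohort". The baseline gift therefore comes before the exposure, and the endline survey comes after it.

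Three places link the gift to what is measured:

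- Sample Size Calculations, planning indicators: "From 24-29% of caregivers reported having a local or shop toy in the home".
- Outcomes and Measures: Caregiver Cohort: child stimulation practices, including play and access to education materials, are one of the three primary outcomes.
- Data Collection: Caregiver Cohort: the caregiver survey covers play within the household environment.

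Under Data Analysis, the effects of radio exposure alone (Objective 1) "will be described by comparing study outcomes at baseline and endline within the MR study group only". Objective 2 is a DID between the radio-only arm (MR) and the full-package arm (MRV-CCD).

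**The concern.** The study places in the home an object of the kind that it may later count. In Objective 1 the gift and the radio campaign both fall between the same two measurements. Every MR cohort caregiver is offered the gift, and the planned analysis has no comparison group without it. Covariate adjustment cannot separate two exposures that everyone shares. The Protocol's question on listenership or recall as dose helps interpretation, but it is observational and does not replace the planned pre-post comparison.

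In Objective 2 one might expect a gift common to both arms to drop out. For an uncapped count of toys it would, if uptake were equal. For a yes/no item it need not, because the arm with fewer owners has more room to move.

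The results are meant to inform decision makers about radio and about the full package. On these items a rise caused by the study's own gift could be reported as a radio effect, and the added value of the full package could be misstated.

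**Working it through.** **Inputs from the Protocol.** Toy baseline 24-29%. Planned radio effect: "With the introduction of radio messaging only, we estimate a 5-10% effect size". Objective 1: 420 evaluable caregivers in MR, McNemar test at the 5% level, and "estimated correlation of 0.4 between respondents at baseline and endline". Objective 2 (Table 4): 430 per arm, MR 10% to 15%, MRV-CCD 25% to 45%, DID 15 points.

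**Assumption.** Let g be the share of homes otherwise lacking the item that have it at endline because of the gift. The Protocol gives no value, so a range is shown. For a yes/no item with endline prevalence e without the gift, the endline with it is e + (1 - e)g.

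**Reproducing the plan.** A two-sided large-sample McNemar calculation with correlation 0.4 gives power 0.801, 0.990 and 0.980 for the three rows of Table 3 (stated 80%, 99%, 98%). 420 × 1.2 / 0.85 = 592.9 (stated 593).

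**Objective 1, zero radio effect.** The change is (1 - p)g, where p is the baseline.

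- 5 points, the low end of the planned effect: g = 0.05/0.76 = 6.6% at p = 24%; g = 0.05/0.71 = 7.0% at p = 29%.
- 10 points, the high end: g = 0.10/0.76 = 13.2%; g = 0.10/0.71 = 14.1%.

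For the test, let p01 and p10 be the no-to-yes and yes-to-no shares and p00 the no-to-no share before the gift. The gift changes them to p01 + g·p00 and p10(1 - g). With n = 420:

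| Baseline | g | Change (points) | Chance of a significant MR result |
|---|---|---|---|
| 24% | 0.05 | 3.8 | 35% |
| 29% | 0.05 | 3.55 | 29% |
| 24% | 0.10 | 7.6 | 85% |
| 29% | 0.10 | 7.1 | 77% |

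The nominal level is 5%.

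**Objective 2, equal g in both arms.**

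- Table 4 values: DID = (0.45 + 0.55g - 0.25) - (0.15 + 0.85g - 0.10) = 0.15 - 0.30g. This is 12, 9 and 6 points at g = 0.1, 0.2 and 0.3.
- Equal 25% baselines, endlines 30% and 45%: DID = 0.15(1 - g). This is 13.5, 12 and 10.5 points.

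**Objective 2, unequal g.** The DID stays at 15 points when 0.55 × g(MRV-CCD) equals 0.85 × g(MR) with Table 4 values, a ratio of 0.85/0.55 = 1.55. With equal baselines the ratio is 0.70/0.55 = 1.27. Above these ratios the gift inflates the DID.

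**Objective 2, power with equal g.** An analytic standard error (430 per arm, Table 4 values, correlation 0.4 assumed to hold after the gift) gives 99.9% without the gift and 97%, 79% and 44% at g = 0.1, 0.2 and 0.3. Carrying the gift through the paired cells instead gives 95%, 72% and 37%. With equal 25% baselines the first method gives 99.3% without the gift and 97%, 93% and 86%. At low g the loss is small.

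**The case against.** **The affected item is inferred.** The toy indicator is a planning figure from the Malezi I evaluation, and the questionnaire is not shown. The endline wording could exclude gifts, ask about source, or record a count, and scoring may be set out elsewhere. This stands as a limit on reach, so the point applies only to items that count the gift. Wording alone would not remove play done with the gift.

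**Objective 1 centres on awareness, and its change is uncontrolled anyway.** Children also grow older between the surveys, so the MR change was never a clean radio effect. Both statements are fair. But Objective 1 also names reported parenting practices, and the gift is a source of bias that the study itself adds and can avoid.

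**g is assumed.** The gift, or the item it supplies, must last through a nine-month exposure plus the survey periods. True, and for that reason results are given over a range.

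**The direction in Objective 2 is open.** A reader might infer that the gift necessarily understates the full package. The documents do not support that. MRV-CCD caregivers receive play counselling and home visits and could plausibly keep the gift more often, and above a ratio of 1.27 to 1.55 the bias reverses.

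**A severe loss of power is not shown.** The Protocol says that "n=430 caregivers per intervention group will provide 90% power to detect a 15" percent DID. Solving back from that 90% gives a standard error of 15/(1.960 + 1.282) = 4.63 points and power of 74%, 49% and 25% at g = 0.1, 0.2 and 0.3. That standard error comes from a simulation whose settings are not given, and the analytic calculation gives about 3.0 points without the gift. The lower series should not be relied on.

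**Conclusion.** The concern holds for toy, book and play-material items that count the gift. For these, the MR-only pre-post change mixes a gift effect with any radio effect. At a 24-29% baseline, g of about 7% is enough to produce the low end of the planned radio effect with no radio effect at all. The chance of a significant result is then well above 5% even at g = 0.05. This rests on an assumed g, a yes/no item, and the Protocol's own n and correlation.

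For Objective 2 the supported conclusion is narrower: an equal offer of the gift does not guarantee that it cancels on yes/no items, and the sign of the resulting bias is unknown. Equal g shrinks the DID; sufficiently higher g in MRV-CCD inflates it.

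Knowledge, discipline and singing items are not directly affected. Reading is touched only indirectly, and only where the gift is a book.

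**What to change.** Give a non-play token of the same value (under USD 5) at baseline in both arms, and hand over the toy only after the endline interview is complete. This keeps the gift budget and changes no sample size, visit or arm. It needs ethics approval of the change, and the baseline thank-you becomes less child-friendly.

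If baseline gifts have already been given:

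- Add one endline question on the source of toys and books.
- Report the affected items with and without study gifts in both arms. Excluding gifts may understate change where the gift displaced a toy that the family would have obtained.
- State the gift, including play or reading done with it, as a limitation of the Objective 1 change and of the DID, with the sign of the latter unknown.

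This second route costs one extra question. It relies on recall and does not remove play done with the gift.
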